**Multiple Interventions During Index Procedure:**

Once stent is placed into the WON, dilation of the AXIOS™ stent is allowed to expand the stent if needed. Dilation can be performed to the maximal diameter of the AXIOS™ stent. A single, 7 fr double pigtail plastic stent (Boston Scientific 7Fr Advanix™ Biliary Stent) may be placed through the AXIOS™ stent at the discretion of the investigator. Access to the WON with a forward viewing diagnostic or therapeutic upper gastroscope is allowed up to 20 minutes (from time of endoscopic access of the WON) to break-up large chunks of necrosis and lavage collection at the discretion of the physician.

WON Resolution Assessment - 7 days (+/- 3 days) for inpatients and 14 (+/- 5 days) days for outpatients (needed until radiographic decrease of WON size to  $\leq$  3cm) – Office/Hospital Visit:

- Cross sectional imaging (CT or MRI) to assess reduction in WON size. If reduction in size is deemed insufficient, necrosectomy will be initiated
- Documentation of clinical improvement defined as improvement of principal WON-related symptoms
- Necrosectomy (as needed)
- Adverse event assessment/device event assessment
- Organ failure assessment (Marshal scoring system)
- Current medication
- Labs (as needed)

Reintervention/Necrosectomy Visits when needed during AXIOS™ stent indwell – Office/Hospital Visit:

- Necrosectomy initiated if WON reduction in size is deemed insufficient during WON Resolution Assessment Visit. Duration of each necrosectomy session is limited to 60 minutes
- Percutaneous drainage or additional endoscopic drainage may be needed if reduction in WON size is insufficient or in cases of continued WON related symptoms such as infection/sepsis despite necrosectomy. Choice of stent (AXIOS™ or plastic double pigtail

stent(s)) for repeat endoscopic drainage procedures will be left to the discretion of the investigator. The double pigtail plastic stent(s) or new AXIOS™ stent may be placed through the tract established by the original AXIOS™ stent or in a separate location.

- Stent lumen patency assessment
- Imaging (as applicable)
- Labs (as needed)
- Adverse event assessment/device event assessment
- Current medication

Stent Removal Visit - between 14 days and 60 days (+/- 7 days) of stent placement – Office/Hospital Visit

- Stent lumen patency assessment
- Stent removal after evidence of clinical and radiographic (via CT or MRI) resolution of WON

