#### Primary Effectiveness Endpoint Assessment:

*Note: Success will be based on the number of WONs resolved, not on the number of AXIOS™ Stents required to achieve resolution.*

- If it is determined that the fluid collection is actually two separate collections, and each collection is drained via an AXIOS™ stent, then each collection will be assessed individually via the drainage success criteria of  $\leq 3$ cm.
- If it is determined that the fluid collection is a single collection but the drainage is inadequate via a single AXIOS™ stent, then the success of the AXIOS™ drainage will be assessed as follows:
  - If a second AXIOS™ stent is used at a new drainage site/original drainage site and the entire fluid collection is drained to meet the success criteria of  $\leq 3$ cm then the collection will be considered to be a single collection drainage success.
  - If a second AXIOS™ stent is used at a new drainage site and the entire fluid collection does not drain adequately to meet the drainage success criteria of  $\leq 3$ cm then the fluid drainage of the collection will be considered to be a single drainage failure.
  - If a plastic stent is used at a new drainage site and the entire fluid collection drains to meet the drainage success criteria of  $\leq 3$ cm then the fluid drainage will be considered indeterminate.

- If a single, 7fr plastic stent is used at the same drainage site, through the AXIOS™ stent, and the entire fluid collection drains to meet the drainage success criteria of  $\leq 3$ cm then the fluid drainage will be considered a single collection drainage success.
- If a plastic stent is used at a new drainage site and the entire fluid collection does not drain to meet the drainage success criteria of  $\leq 3$ cm then the fluid drainage will be considered a single drainage failure.

Hypothesis:

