#### Data Analysis:

Descriptive statistics will be presented for all ITT and treated subjects. If the treated and PP cohorts are different, the primary effectiveness and safety endpoints will be assessed for the PP cohort. The mean, standard deviation, minimum, and maximum will be used to describe continuous variables; the median (and interquartile range) will be calculated where appropriate. Frequency tables will be used to summarize discrete variables. Proportions of subjects with adverse events and SAEs will be reported.

Interim Analysis:

No formal interim analyses are planned for the purpose of stopping this study early. Informal interim analysis may be conducted for the purpose of submissions of abstracts to major professional meetings.

Subgroup Analysis:

There are no planned subgroup analyses.

Justification of Pooling:

The analyses will be performed using data pooled across institutions and whether patients had a double pigtail plastic stent placed within the Axios stent. An assessment of the poolability of subjects across sites (double pigtail plastic stent groups) for the primary effectiveness and safety endpoints will be made by fitting logistic regression models with site (double pigtail plastic stent) as a factor and the primary effectiveness and safety endpoints as outcomes. Certain baseline variables may also be explored for pooling.

If the P value for the site (double pigtail plastic stent) is  $\geq 0.05$ , it will be concluded that the endpoint is not different across sites (double pigtail plastic stent groups), and the data can be pooled. If the P value for site (double pigtail plastic stent) from the logistic model is  $< 0.05$ , site (double pigtail plastic stent group) differences will be explored.

Multivariable Analyses:

No multivariable analyses are planned for this study.

Changes to Planned Analyses:

Any changes to the planned statistical analyses made prior will be documented in an amended Statistical Analysis Plan. Changes from the planned statistical methods after performing the analysis will be documented in the clinical study report along with a reason for the deviation.

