5.3 Subgroup Analyses

No subgroup analysis is planned.

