5.4 Justification of Pooling

The analyses will be performed using data pooled across institutions. An assessment of the poolability of subjects across sites for the primary effectiveness and safety endpoints will be made by fitting logistic regression models with site as a factor and the primary effectiveness and safety endpoints as outcomes. Certain baseline variables may also be explored for pooling.

If the P value for the site is ≥ 0.05 , it will be concluded that the endpoint is not different across sites, and the data can be pooled. If the P value for site from the logistic model is < 0.05 , site differences will be explored.

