9. REVISION HISTORY

Document Revision Number	Template Number and Version	Section	Change	Reason for Change
A	90702621, AE	All	Original version of the SAP

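### SAP 5.4 omits the plastic-stent pooling check that protocol 7.4 requires, and both documents read P ≥ 0.05 as no difference, which 40 patients cannot support for moderate differences

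*SAP*

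**What the plan says.** Protocol 7.4, under Justification of Pooling, covers two factors: "The analyses will be performed using data pooled across institutions and whether patients had a double pigtail plastic stent placed within the Axios stent". It fits logistic models for both primary endpoints with site, and likewise plastic stent, as the factor. When P reaches 0.05 or more, the protocol states: "it will be concluded that the endpoint is not different across sites (double pigtail plastic stent groups), and the data can be pooled". Below that threshold, the differences are explored. The protocol's revision history shows that the stent factor entered at Rev. H in response to FDA feedback.

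SAP 5.4 carries the same rule for site alone: "An assessment of the poolability of subjects across sites for the primary effectiveness and safety endpoints will be made". If P ≥ 0.05, "it will be concluded that the endpoint is not different across sites, and the data can be pooled". SAP 5.3 adds "No subgroup analysis is planned". The SAP's only plastic-stent rules (sections 1 and 3.1) concern a stent at a new drainage site.

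The protocol does provide for a plastic stent inside the AXIOS stent. At the index procedure, one "may be placed through the AXIOS™ stent at the discretion of the investigator" (section 6.3). In section 7.1, the case that begins "If a single, 7fr plastic stent is used at the same drainage site, through the AXIOS™ stent" counts as a drainage success if the collection shrinks to 3 cm or less.

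SAP 4.1 says that no hypothesis tests will be done, yet SAP 5.4 applies a 0.05 rule. Neither document says which P value from the logistic model is meant.

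**The concern.** The primary resolution rate mixes patients drained through AXIOS alone with patients who also had a plastic stent inside it. The pooling check in protocol 7.4 is the only planned analysis that separates them, and the SAP does not contain it.

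The decision rule also treats failure to reject as evidence of homogeneity. In a study whose size was set without a statistical calculation, a non-significant result is likely even when groups differ by an amount that a clinician would care about. The report could then state that sites or stent groups do not differ when the data leave wide room for a difference.

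**Working it through.** **Inputs from the documents.** N = 40; expected related-SAE rate similar to 10% (3/30 in the original IDE); expected resolution 70%; up to 6 sites with no cap per site; threshold 0.05.

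**Assumptions, because the documents do not give them.** Stent-group split from 10/30 to 30/10; six near-equal sites of 7, 7, 7, 7, 6, 6, with other layouts as stated; the sizes of the true differences.

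**1. The plan's own figures.** Clopper-Pearson for 3/30 gives 2.1% to 26.5%, as stated. Expected SAE patients: 0.10 × 40 = 4. Expected resolutions: 0.70 × 40 = 28.

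**2. Power by stent group.** Score (Pearson) test, exact enumeration over both binomials, two-sided 0.05. The first group has the higher rate.

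| Split | Resolution 80% v 60% | Resolution 90% v 50% | SAEs 20% v 5% |
|---|---|---|---|
| 10/30 | 0.19 | 0.68 | 0.29 |
| 15/25 | 0.27 | 0.81 | 0.34 |
| 20/20 | 0.29 | 0.84 | 0.29 |
| 25/15 | 0.31 | 0.85 | 0.20 |
| 30/10 | 0.26 | 0.76 | 0.08 |

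Roughly 80% power for resolution therefore needs a gap of about 40 points. By the usual normal approximation, 80% power for 80% against 60% would need 82 patients per group.

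**3. Power by site.** For resolution, with three sites at 80% and three at 60%, power is 0.13 (score) to 0.22 (likelihood ratio, LR). For SAEs, with one of six sites at 30% and the rest at 6%, it is 0.16 (LR) to 0.22 (score). With only three sites the latter rises to 0.41 (score) to 0.50 (LR).

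**4. What the rule would report.** Take a hypothetical 16/20 resolved with the plastic stent and 12/20 without.
- Pooled: 28/40 = 70%, above the 67% criterion.
- Score statistic: 0.20² / [0.70 × 0.30 × (1/20 + 1/20)] = 0.04 / 0.021 = 1.90, so P = 0.17. LR gives 0.16, Wald 0.17, Fisher 0.30.
- Difference: 20 points, Newcombe 95% CI −8 to 44.
- Exact 95% CIs: 56% to 94% and 36% to 81%.

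The SAP would show none of this. Protocol 7.4 would report no difference under any of the four tests.

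**5. Why the type of P value matters.** At a uniform 10% SAE rate, the chance that at least one of the six sites has no SAE is

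1 − (1 − 0.9⁷)⁴ × (1 − 0.9⁶)² = 1 − 0.5217⁴ × 0.4686² = 0.98.

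It is 0.82 for four sites and 0.57 for three. When a site has no event, its log-odds estimate diverges, its standard error grows faster, and the Wald statistic collapses.

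Suppose all 4 SAEs fall at one site of 7. The score statistic is (4 − 0.7)²/0.63 + 3 × 0.7²/0.63 + 2 × 0.6²/0.54 = 17.29 + 2.33 + 1.33 = 20.95 on 5 df, so P = 0.0008. LR gives P = 0.006 and the exact conditional test 0.0019. The joint Wald P is about 1. The same data are flagged or called not different, depending on which line of output is read.

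**The case against.** The strongest reply is that little depends on this check. Pooling happens whatever the P value, P < 0.05 only triggers exploration, and the study has no formal hypothesis. That stands, and it limits the point to a reporting matter.

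A reader might infer more in several places, and the documents do not support it:

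- **That AXIOS alone would fail in the example.** The 67% criterion applies to the pooled rate; no criterion applies to a stent group. Placement is the investigator's choice, so any difference between stent groups is confounded by the reason for placing the stent.
- **That the check can detect nothing.** It can detect large gaps, as the 90% against 50% column shows.
- **That the stent group should be defined by index placement only.** Protocol 7.4 has no such limit, and section 6.3 allows plastic stents through the original tract later. An index-only definition would move those patients into the AXIOS-alone group.
- **That the score test should be mandatory.** With an affected site of 12 patients, power for SAEs of 30% against 6% is 0.12 for score and 0.21 for LR, while the LR type I error there is only about 3% at a common 10% rate. On the other hand, LR reaches 9.7% for SAEs by stent group at some splits. Neither test is clearly better; only the case against Wald is clear.
- **That the SAP is out of date.** Its revision history lists only "Original version of the SAP", but the text available carries no SAP date. The omission stands without that inference.

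**Conclusion.** The point holds at moderate weight. The mismatch between SAP 5.4 and protocol 7.4 is plain from the two texts and needs no calculation. The no-difference conclusion is unsupported for moderate effects under every stent split examined: power does not exceed 0.31 for a 20-point difference in resolution, or 0.34 for SAEs of 5% against 20%. These figures rest on assumed splits and differences, because the documents give none.

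It would be wrong to conclude that the primary results are at risk. The pooled rates, their Clopper-Pearson intervals and the 67% and 17.5% decisions are the same with or without this check. What is affected is the homogeneity statement and whether readers see results by stent group.

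**What to change.** 1. Add to SAP 5.4 the plastic-stent comparison for both primary endpoints as protocol 7.4 defines it: any double pigtail stent placed within the AXIOS stent. Break it down into none, placed at the index procedure, and placed later, because later placement can follow inadequate drainage. State that the comparison is descriptive and confounded by investigator choice.
2. In SAP 5.4 and protocol 7.4, replace the no-difference conclusion with: *no strong evidence of heterogeneity was found; the study has little power to detect moderate differences*.
3. Whatever the P value, report counts and rates of both primary endpoints by site and by stent group with Clopper-Pearson 95% intervals, the method the plan already uses.
4. State that the Wald P value will not be used, and name one other test (LR, score or exact) in advance. The choice can be left to the sponsor's statistician.
5. Reconcile the statement in SAP 4.1 that no hypothesis tests will be done with the P-value rule in 5.4.

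Cost: a SAP amendment under SAP 5.7, one extra table, and one sentence in the protocol, which can wait for the next amendment; if the change is judged to affect scientific integrity, the approvals in protocol section 9 apply. No new patient assessments are needed. The schedule in protocol 6.1 has no row for the plastic stent, so confirm that the eCRF records its placement and timing. The downside is a less reassuring poolability statement.

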5.5 Multivariable Analyses

No multivariable analyses are planned for this study.

5.6 Other Analyses

5.6.1 Baseline Characteristics

Baseline data will be summarized to assess subject demographics, clinical history, risk factors, and pre-procedure characteristics. Data will be summarized as described in Section 4.1.

5.6.2 Post-procedural Information

Post-procedure information will be collected at regularly scheduled follow-up examinations as detailed in the clinical study event schedule and will be summarized using descriptive statistics for continuous variables (e.g., mean, standard deviation, n, minimum, maximum) and frequency tables or proportions for discrete variables. No formal statistical testing will be performed. Data will be summarized as described in Section 4.1.

5.6.3 Subject Disposition

Subject disposition (e.g., number completing the study, number lost-to-follow-up) will be summarized with frequency tables for each visit.

5.7 Changes to Planned Analyses

Any changes to the planned statistical analyses made prior will be documented in an amended Statistical Analysis Plan. Changes from the planned statistical methods after performing the analysis will be documented in the clinical study report along with a reason for the deviation.

6. VALIDATION

All clinical data reports generated per this plan will be validated per 90702587, Global WI: Clinical Data Reporting Validation.

7. PROGRAMMING CONSIDERATIONS

7.1 Statistical Software

Statistical data review will be performed by the sponsor. Statistical analyses will be performed using SAS System software, version 9.2 or later (Copyright © 2000 SAS Institute Inc., [name], USA. All rights reserved).

SF-12 survey data will be evaluated using the PRO CoRE software version 1.2 (April, 2018, Optum Inc., Johnston, Rhode Island 02919, USA).

7.2 Format of Output

Results of analysis will be output programmatically to Word documents from SAS with no manual intervention. All output for the final statistical report will be in the form of a Word document containing tables, figures, graphs, and listings, as appropriate.

9. REVISION HISTORY

Document Revision Number	Template Number and Version	Section	Change	Reason for Change
A	90702621, AE	All	Original version of the SAP
